2.1.3 Rationale for a Randomized Trial among Hospitalized Patients

The initial symptoms of COVID-19 develop approximately 2-10 days after infection with the SARS-CoV-2 virus,²³ with the progression to respiratory failure and ARDS occurring approximately 7-10 days after the onset of symptoms.²⁴ While most adults with COVID-19 recover without complications, patients who require hospitalization experience high rates of complications. In case series of hospitalized patients with COVID-19, up to 26% require ICU admission and up to 17% die in the hospital.^{24,25} The period between onset of symptoms and development of severe respiratory failure represents a potential window for treatment of hospitalized patients to prevent disease progression.

Given the unprecedented public health crisis caused by COVID-19, there is significant interest in finding effective therapies and, specifically, in repurposing approved medications with widespread availability and known safety profiles.^{3,26} Potential therapies that are being considered include hydroxychloroquine, chloroquine, lopinavir/ritonavir, interferon β , and corticosteroids. Despite extremely limited clinical data, hydroxychloroquine has been adopted into treatment guidelines in China²⁷ and has been proposed as first-line therapy for hospitalized patients in institutional protocols for COVID-19 at some hospitals in the US.

Data on the safety and efficacy of hydroxychloroquine from randomized trials is urgently needed. A randomized clinical trial demonstrating that hydroxychloroquine prevents disease progression in hospitalized patients with COVID-19 would provide evidence-based therapy for an ongoing pandemic. A randomized clinical trial demonstrating that hydroxychloroquine is ineffective against COVID-19 would also have important public health impacts. Hydroxychloroquine is known to be associated with a risk of QT prolongation, seizure, bone marrow suppression, and neuromyopathy. Risks of hydroxychloroquine may increase in patients with decreased renal function and critical illness, as may occur in COVID-19. It also interacts with many medications commonly administered to hospitalized and critically ill patients. If hydroxychloroquine is not effective at treating COVID-19, patients should not be exposed to these potential toxicities. Additionally, prior trials have suggested that hydroxychloroquine may worsen outcomes for some viral infections. In a placebo-controlled trial of hydroxychloroquine for HIV treatment, it caused significantly higher HIV viral loads and lower CD4 counts.²⁸ A related drug, chloroquine, was shown to delay the immune response to Chikungunya infection and lead to higher viral loads and more lymphopenia in a non-human primate model.²⁹

Given the need for effective treatments of COVID-19, the unclear efficacy and safety of hydroxychloroquine as a treatment of COVID-19, and the widespread clinical use of hydroxychloroquine during the current pandemic, a randomized clinical trial is urgently needed.

2.1.4. Rationale for Evaluating Hydroxychloroquine Monotherapy

In addition to hydroxychloroquine, several other medications have been proposed as potential therapies for COVID-19, including remdesivir and azithromycin. Remdesivir treatment for COVID-19 is being studied in a clinical trial sponsored by the National Institute of Allergy and Infectious Diseases (NIAID) [NCT04280705]. Azithromycin is a macrolide antibiotic that is commonly used in the US for treatment of respiratory infections. During the design of this protocol, the investigators considered studying combination therapy of hydroxychloroquine plus remdesivir and hydroxychloroquine plus azithromycin. The investigators noted that combination therapy would likely increase the risk of toxicities. With no preliminary data suggesting combination therapy is likely to be more effective than hydroxychloroquine monotherapy, the investigators believe the risks of studying combination therapy likely outweigh the benefits at this time. Additionally, results of a trial evaluating combination therapy may be difficult to interpret. Trial results suggesting effectiveness would probably not be attributable to a single agent and would leave uncertainty about whether treatment with combination therapy is preferable to monotherapy. Furthermore, null results of a trial evaluating combination therapy could occur if neither agent is effective, if one is effective and one is detrimental, or if both are effective but there are unfavorable drug-drug interactions. Interpretation of a trial of one agent will be straightforward and may provide the basis for subsequent trials of combination therapy. The investigators note that two distinct, simultaneously conducted placebo-controlled randomized trials evaluating remdesivir and hydroxychloroquine separately will provide high quality data on the effectiveness and safety of each agent versus placebo.

2.2 Study Aims

2.2.1 Study aim

To compare the effect of hydroxychloroquine versus placebo on clinical outcomes, measured using the COVID Ordinal Outcomes Scale at Day 15, among adults with COVID-19 requiring hospitalization.

2.2.2 Study hypothesis

Among adults hospitalized with COVID-19, administration of hydroxychloroquine will improve clinical outcomes at Day 15.

2.3 Study Design

We will conduct an investigator-initiated, multicenter, blinded, placebo-controlled, randomized clinical trial evaluating hydroxychloroquine for the treatment of adults hospitalized with COVID-19. Patients, treating clinicians, and study personnel will all be blinded to study group assignment.

3. STUDY POPULATION AND ENROLLMENT

3.1 Inclusion Criteria

1. Age \geq 18 years
2. Currently hospitalized or in an emergency department with anticipated hospitalization.

3. Symptoms of acute respiratory infection, defined as one or more of the following:
 - a. Cough
 - b. fever ($> 37.5^{\circ}\text{C}$ / 99.5°F)
 - c. shortness of breath (operationalized as any of the following: subjective shortness of breath reported by patient or surrogate; tachypnea with respiratory rate ≥ 22 /minute; hypoxemia, defined as $\text{SpO}_2 < 92\%$ on room air, new receipt of supplemental oxygen to maintain $\text{SpO}_2 \geq 92\%$, or increased supplemental oxygen to maintain $\text{SpO}_2 \geq 92\%$ for a patient on chronic oxygen therapy).
 - d. sore throat
4. Laboratory-confirmed SARS-CoV-2 infection within the past 10 days prior to randomization

3.2 Exclusion Criteria

1. Prisoner
2. Pregnancy
3. Breast feeding
4. Unable to randomize within 10 days after onset of acute respiratory infection symptoms
5. Unable to randomize within 48 hours after hospital arrival
6. Seizure disorder
7. Porphyria cutanea tarda
8. $\text{QTc} > 500$ ms on electrocardiogram within 72 hours prior to enrollment
9. Diagnosis of Long QT syndrome
10. Known allergy to hydroxychloroquine, chloroquine, or amodiaquine
11. Receipt in the 12 hours prior to enrollment, or planned administration during the 5-day study period that treating clinicians feel cannot be substituted for another medication, of any of the following: amiodarone; cimetidine; dofetilide; phenobarbital; phenytoin; sotalol
12. Receipt of > 1 dose of hydroxychloroquine or chloroquine in the 10 days prior to enrollment
13. Inability to receive enteral medications
14. Refusal or inability to be contacted on Day 15 for clinical outcome assessment if discharged prior to Day 15
15. Previous enrollment in this trial
16. The treating clinical team does not believe equipoise exists regarding the use of hydroxychloroquine for the treatment of this patient

3.3 Justification of Exclusion Criteria

The exclusion criteria are primarily designed for patient safety. In addition to excluding specific vulnerable populations (e.g., prisoners), these criteria are designed to exclude patients for whom receipt of hydroxychloroquine might increase the risk of serious adverse events. For example, patients who have a prolonged QTc or are taking medications that would increase the risk of experiencing a prolonged QTc when combined with hydroxychloroquine are excluded to minimize the risk of Torsades de Pointes.

3.4 Screening

The site investigator or delegate will screen for hospitalized patients with laboratory confirmed COVID-19 (that is, a positive laboratory test for SARS-CoV-2) or a pending SARS-CoV-2 test. Treating clinicians will also be instructed to contact the site investigator or delegate for patients with a high clinical suspicion of COVID-19.

3.5 Assessment of Eligibility and Exclusion Tracking

For patients who appear to meet inclusion criteria during screening, an electronic case report form will be completed to determine eligibility and track exclusions. The electronic case report form will be accessed and stored in the electronic database. At the time of entry into the screening database, the patient will be assigned a screening number.

If a patient appears to meet all eligibility criteria, the site investigator or delegate will approach the treating clinician to ask permission to approach the patient or Legally Authorized Representative (LAR) to confirm eligibility, discuss potential study recruitment, and proceed with informed consent.

For all excluded patients, including refusal by the treating clinician or patient/surrogate, a small number of de-identified variables will be collected including month and year the patient met screening criteria, age, sex, ethnicity, patient location, and reason(s) patient was excluded. For the safety of research personnel and conservation of personal protective equipment, these encounters may occur via telephone or videophone.

3.6 Process of Obtaining Informed Consent

Informed consent will be obtained from the patient or from a surrogate decision maker if the patient lacks decision-making capacity.

In some instances, bringing a paper consent form and pen to the bedside of a patient with known or suspected COVID-19 and then taking these out of the room would violate infection control principles and policies. Given the infectious risk from COVID-19 and potential shortages of personal protective equipment (PPE), there is a moral and practical imperative to minimize face-to-face contact between patients and non-clinical personnel. The current epidemic also presents unique challenges to obtaining consent from participant's legally authorized representative (LAR). To minimize infectious risk, many institutions are not allowing visitors to enter the hospital. Furthermore, the LAR is likely to have been exposed to the patient and may therefore be under self-quarantine at the time of the informed consent discussion.

Therefore, in addition to the traditional approach of an in-person consent discussion and signed paper informed consent document, we will allow use of "no-touch" consent procedures for this trial. Below, we outline three examples of no-touch consent procedures that may be used: (a) a paper-based approach; (b) an electronic/e-consent approach; and (c) attestation of informed consent.

3.6.1 Paper-based approach

1. The informed consent document is delivered to the patient or LAR.
 - a. If the patient or LAR is on-site, the informed consent document may be delivered to the patient or LAR either by research staff or by clinical staff
 - b. If the LAR is off-site, the informed consent document may be emailed, faxed, or otherwise electronically transferred to the LAR (method dictated by institutional policy)
2. Research staff discuss the informed consent document with the patient or LAR either in-person or by telephone or videophone. *This step confirms subject/LAR identity.*

3. If the patient or LAR decides to consent to participate, the patient or LAR signs the paper copy of the informed consent document.
4. A photograph is taken of the signature page of the informed consent document and uploaded into the electronic database (e.g. REDCap).
 - a. If using the patient's device (such as a patient's personal cellular phone), a survey link can be sent to their device to allow direct upload of the image into the electronic database (e.g. REDCap).
 - b. If using a staff device, it must be approved to store PHI by the local institution. In that case, research personnel can take a photograph of the signature page of the informed consent document either directly or through the window or glass door leading into the patient's room. The photograph can then be uploaded into the electronic database. If a staff device is taken into the patient's room to take a photograph it must be able to be disinfected according to local institutional practices.
5. Research staff and witness provide signatures within the electronic database (e.g. REDCap) confirming their participation in the informed consent process.
6. The patient or LAR retains the paper consent document. The image of the signature page may be printed and bundled with a copy of the blank informed consent document for research records.

3.6.2 Electronic/e-consent approach

1. The electronic informed consent document is opened on a research device or a link for the electronic informed consent document is sent to the patient's or LAR's device.
2. Research staff discuss the informed consent document with the patient or LAR either in person or by telephone or videophone. *This step confirms subject/LAR identity.*
3. If the patient or LAR decides to consent to participate the patient or LAR signs the electronic informed consent document. This signature may be either:
 - a. an actual signature (often tracing a finger on the screen) OR
 - b. a username and password specific to the individual signing
4. Research staff and witness provide signatures within the electronic database (e.g., REDCap) confirming their participation in the informed consent process.
5. The image of the signature page may be printed and bundled with a copy of the blank informed consent document for research records.

If a hospital device is provided to facilitate electronic or paper-based consent, that device will be disinfected according to institutional protocols and removed by research staff or clinical staff during the next entry into the patient's room.

This approach complies with relevant regulations and sub-regulator guidance at 45 CFR 46.117, 45 CFR 164.512, 21 CFR 11 Subpart C (11.100–11.300), <https://www.hhs.gov/ohrp/regulations-and-policy/guidance/use-electronic-informed-consent-questions-and-answers/index.html>, <https://www.fda.gov/regulatory-information/search-fda-guidance-documents/informed-consent>

The information for the informed consent discussion will be provided in a formal document (or electronic equivalent) that has been approved by the IRB and in a language comprehensible to the potential participant, using an interpreter if necessary. The information presented in the consent form and by the research staff will detail the nature of the trial and what is expected of participants, including any

potential risks or benefits of taking part. It will be clearly stated that the participant is free to withdraw from the trial at any time for any reason without prejudice to future care, and with no obligation to give the reason for withdrawal. Where a patient does not speak English, a short-form consent and qualified interpreter will be employed, using similar “no-touch” principles. Use of an interpreter and the interpreter’s identity will be documented on the electronic consent.

3.6.3 Attestation of informed consent

If none of the options outlined above (traditional signature and storage of a paper consent form, electronic photographs of a signed consent page, or e-consent) are available, study personnel may attest to completion of the informed consent process using the procedures outlined below. Importantly, the process of informed consent using this attestation option should not change compared with the traditional method of obtaining informed consent for trial participation except for the method of documenting the consent process in the research record. Rather than storing a paper document with the participant’s signature, a member of the research team and an impartial witness will attest to completion of the informed consent process and that the participant signed the informed consent document. This option of attestation of informed consent is not available when obtaining consent through an LAR.

Procedures for attestation of informed consent:

1. An unsigned paper consent form is provided to the patient by a health care worker or study member.
2. The study member obtaining consent arranges an in-person meeting or three-way call or video conference with himself/herself, the patient, and an impartial witness. If desired and feasible, additional people requested by the patient (e.g., next of kin) may also join this discussion.
3. Study member reviews consent and answers questions in the presence of the impartial witness.
4. Patient signs the paper informed consent document while the witness is listening on the phone or directly observing.
5. Patient provides verbal confirmation that he/she would like to participate in the trial and he/she has signed and dated the informed consent document. This signed informed consent document stays with the patient due to the risk of spreading the virus.
6. Study member and witness attest that other techniques for documenting informed consent were not available for this participant and that the participant provided written informed consent for trial participation by signing a paper informed consent document. An attestation form is available in the ORCHID REDCap toolkit for documenting this attestation. This attestation page with signatures from the study member and witness will be save as evidence of the informed consent process. A signature from the participant will not be saved in the research record.

3.7 Randomization and Blinding

Participants confirmed to meet all eligibility criteria who have provided informed consent will be randomized 1:1 to hydroxychloroquine versus placebo. A randomization code will be provided to the site investigator or delegate from a centralized, web-based platform. Randomization will require provision of the screening number and confirmation of patient eligibility.

Randomization will be completed in permuted blocks of varying size and stratified by site. The randomized sequence allocation will be stored on a secure server and will not be available to site study personnel. Site research personnel will have a unique Personal Identification Number (PIN) to access the

randomization system. Each subject will receive a computer-generated randomization ID number. The computer-generated randomization ID number will be provided to the pharmacy who will provide a dose pack containing hydroxychloroquine or placebo. The participant, treating clinicians, study personnel, and outcome assessors will all remain blinded to group assignment until after the database is locked and blinded analysis is completed.

3.8 Minorities and Women

No patients will be excluded on the basis of race, ethnicity, or sex. The clinical coordinating center will monitor recruitment of minorities and women. If necessary, additional recruitment efforts will be made to ensure that the aggregate patient sample contains representative race/ethnicity and sex subsets.

4. STUDY INTERVENTIONS

4.1 Treatment of Study Participants

A summary of the trial's schedule of events is included in Appendix A.

Timing of study procedures is based on the time of randomization, which is defined as "Time 0". The primary outcome will be assessed on Study Day 15, which corresponds to 14 days (2 weeks) after randomization.

Study medications will be administered by clinical or research personnel while the patient is hospitalized. The first dose of study medications will be administered within 4 hours of randomization. In the hospital, medication delivery after the first dose will correspond to the timing of morning and evening medication delivery for the hospital/unit. If the patient is discharged prior to completion of the study medication, the patient will be discharged with the study medication packet to complete the course after discharge. At home, the patient will be instructed to take the morning dose upon awakening and the evening dose approximately 12 hours later.

On Study Days 1-5, study personnel will review patient records to confirm administration of study drug and document the number and reason for any missed doses. For patients who are discharged prior to Day 5, study personnel will obtain data on study drug adherence and safety outcomes from the patient or surrogate at via telephone follow-up scheduled at Day 8. Research personnel will also assess patients at Day 15 and Day 29; these assessments will be completed by phone if the patient has been discharged from the hospital.

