4.5 On-Study Monitoring

All patients enrolled in the study will be initially hospitalized and will therefore receive monitoring as a part of routine clinical care, including monitoring by their physicians, nurses, respiratory therapists, and ancillary staff.

In addition to routine clinical monitoring, enrolled patients will have an assessment of the QTc with an electrocardiogram (EKG) or rhythm strip performed 24-48 hours after administration of the first study medication. If an EKG or rhythm strip has been performed as a part of clinical care during this window, study personnel will assess the QTc on these clinically performed tracings. If an EKG or rhythm strip has not been performed as a part of clinical care during this window, an EKG or rhythm strip will be ordered and performed as a part of study procedures. This QTc will be used to monitor patient safety and inform stopping of the study drug as described below. If a patient is discharged from the hospital before the QTc is evaluated at 24-48 hours, the study drug may be continued after discharge without this assessment.

Between randomization and Day 5, study personnel will review the electronic health record daily for potential medication interactions with hydroxychloroquine (see Appendix B). If a medication that is considered to be contraindicated with hydroxychloroquine is discovered, treating clinicians will be contacted to discuss if stopping study drug is appropriate or if the medication in question can be stopped or substituted. If a medication with a potential interaction with hydroxychloroquine is identified, study

personnel will contact treating clinicians to ensure they are aware of the potential interaction. Treating clinicians will determine whether an alternative medication would be appropriate or whether the risk-benefit ratio favors continuing the medication with the known potential interaction. If a patient is started on a medication listed in Appendix B that potentially prolongs the QTc, study personnel will recommend to treating clinicians use of continuous cardiac monitoring when available during the study drug treatment period.

In addition to manual monitoring by study personnel for medication interactions, many electronic health records contain tools within the electronic order entry system to automatically screen for medication interactions with hydroxychloroquine and notify ordering providers of the potential interaction at the time of order entry.

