4.6 Criteria for Stopping Study Drug

Administration of the blinded study drug may be stopped temporarily or permanently for (a) adverse events, (b) results of on-study monitoring, (c) clinical deterioration, or (d) evidence of an alternative cause to the patient's symptoms.

If a patient experiences an adverse event that the patient (or legally authorized representative), treating clinicians, or investigators feel merits temporarily or permanently stopping the study drug, the study drug will be stopped. The explanation for stopping the study drug will be recorded in the case report form, and the adverse event will be recorded and reported according to the adverse event guidelines below. If the adverse event resolves to the extent that the patient (or legally authorized representative), treating clinicians, and investigators feel that resuming the study drug is appropriate, the study drug will be resumed, and this information will be recorded in the case report form.

If a QTc assessed after randomization is >500 ms, the study drug will be discontinued for 24 hours and a repeat EKG will be performed daily until either the QTc is less than 500 ms, at which time study drug is resumed until 5 days after randomization with daily QTc assessments, or until 5 days after randomization is reached without resumption of study drug. Both the value for the QTc and the decision to continue or stop the study drug will be recorded in the case report form. If the QTc in hospitalized patients cannot be assessed at 24-48 hours, study drug will be discontinued until the QTc can be assessed. If the daily on-study monitoring by study personnel for medication interactions indicates a potential interaction with a medication that treating clinicians feel is required for the optimal treatment of the patient and with which treating clinicians and the investigator feel it would be unsafe to administer hydroxychloroquine (including but not limited to: amiodarone; cimetidine; chloroquine; dofetilide; phenobarbital; phenytoin; sotalol), the study drug will be stopped and the reason will be recorded in the case report form.

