9.2 Minimization of Risk

Federal regulations at 45 CFR 46.111(a)(1) require that risks to participants are minimized by using procedures which are consistent with sound research design. This trial protocol incorporates numerous design elements to minimize risk to patients that meet this human subject protection requirement. Hydroxychloroquine has been approved by the Food and Drug Administration and has been used in clinical practice for decades in a number of patient populations with an established safety profile. The dose and route of administration of hydroxychloroquine in this trial are comparable to the dose and route of administration approved for the treatment of other acute infections, such as malaria. The duration of treatment in this trial of 5 days is significantly shorter than for treatment of rheumatologic conditions, for which the drug is frequently administered for multiple years. To further mitigate risk, we will exclude patients with specific risk factors for adverse events from hydroxychloroquine including patients with prolonged QTc, patients receiving medications that may interact with hydroxychloroquine to prolong the QTc, patients with seizure disorder, and patients with porphyria cutanea tarda. The trial protocol includes

on-study monitoring to minimize the risk to patients during therapy. This monitoring includes assessment of QTc after receipt of study drug with specific criteria at which the study drug would be stopped. This monitoring also includes both automated electronic health record and manual study personnel review for medications with potential interactions with hydroxychloroquine during the 5-day study period. The trial protocol includes monitoring of adverse events, clinical outcomes, and interim analyses by an independent data and safety monitoring board empowered to stop or modify the trial at any time.

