14. APPENDICES

Appendix A. Schedule of Events

Study Activity	Pre-Enrollment	Day 1	Day 2	Day 3	Day 4	Day 5	Day 8	Day 15	Day 29	3 Months	6 Months	12 Months
Eligibility assessment	X											
EKG	X		X ^a									
Pregnancy test (if applicable)	X											
Informed consent	X											
Demographic and baseline variable collection		X										
Randomization		X										
Study drug delivery		X	X	X	X	X						
Assessment for study drug adherence		X	X ^a	X ^a	X ^a	X ^a	X ^b					
Safety monitoring for adverse events		X	X ^a	X ^a	X ^a	X ^a	X ^b	X ^b	X ^b			
Assessment of COVID ordinal outcome score	X		X ^a	X ^a	X ^a	X ^a	X ^b	X ^b	X ^b			
Mortality assessment								X ^b	X ^b			
28-day in-hospital outcomes (chart review)									X			
Long-term outcomes										X ^c	X ^c	X ^c

- a. Assessed only if patient remains hospitalized.
- b. Assessed by telephone follow-up if the patient has been discharged.
- c. Assessed in selected patients in-person, or by telephone or videophone.

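### Protocol 4.1 sends remaining study drug home at discharge without exception, which leaves two QTc-related discharge states in conflict with 4.5 and 4.6

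*Protocol*

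**What the plan says.** Protocol 4.1, on a patient who leaves hospital before the last dose: "the patient will be discharged with the study medication packet to complete the course after discharge". The sentence is unconditional and points to no other section.

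Protocol 4.6 sets two QTc rules.

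- The first begins "If a QTc assessed after randomization is >500 ms" and continues "the study drug will be discontinued for 24 hours and a repeat EKG will be performed daily". Its endpoint is either a QTc below 500 ms, "at which time study drug is resumed until 5 days after randomization with daily QTc assessments", or the end of the 5 days with no resumption. It is not limited to inpatients.
- The second covers a missing tracing: "If the QTc in hospitalized patients cannot be assessed at 24-48 hours, study drug will be discontinued until the QTc can be assessed".

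Protocol 4.5 adds an allowance. If discharge comes before the 24-48 h QTc has been evaluated, "the study drug may be continued after discharge without this assessment".

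On monitoring after discharge, Appendix A shows one on-study EKG, at Day 2, with the footnote "Assessed only if patient remains hospitalized". The telephone assessments in 6.3.1 contain no EKG item, and the first call window opens on Day 8. Section 9.2 lists QTc monitoring among the risk safeguards: "This monitoring includes assessment of QTc after receipt of study drug with specific criteria at which the study drug would be stopped".

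**The concern.** A QTc above 500 ms is the only numeric toxicity threshold for stopping drug in 4.6. The sections that act on it were written for a patient who stays in hospital, while 4.1 was written for one who leaves. Nothing joins the two. Dose packs hold all 10 doses from randomization (4.2), so the unused doses are at hand when the patient goes home.

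Some patients can therefore be dosed at home under conditions that 4.6 did not allow in hospital, and sites may settle the matter differently. Detection would be late: adherence after discharge is first asked about at the Day 8 call, when the 5-day course is over.

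**Working it through.** There is no planned figure to reproduce. The check sets the rules side by side for each discharge state.

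| State at discharge | 4.1 | 4.5 allowance | 4.6 | QTc check provided after discharge |
|---|---|---|---|---|
| (a) Resumed after QTc >500 ms | Complete course at home | Does not apply: QTc was evaluated | Daily QTc to 5 days after randomization | None |
| (b) Stopped, 24-48 h QTc not obtained | Complete course at home | Can be read to apply | Stopped until QTc can be assessed | None |
| (c) Still on hold for QTc >500 ms | Complete course at home | Does not apply: QTc was evaluated | No resumption without QTc <500 ms | None |

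**State (a).** Under the procedures the protocol schedules, 4.1 and 4.6 cannot both be met. Continuing at home without tracings departs from 4.6, and keeping the packet back departs from 4.1. Arranging a tracing after discharge is neither provided for nor excluded.

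**State (b).** Two ambiguities combine.

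1. The words in 4.6 about hospitalized patients may describe the patient when the tracing was missed, so that the stop persists after discharge. Or they may be a continuing condition, so that it lapses on discharge.
2. The condition in 4.5 may mean leaving before the 48 h window closes, or leaving at any time with no QTc evaluated.

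On the second reading of both, the patient moves from stopped to permitted with no new information. On the first reading of both, the stop stands and 4.1 contradicts it.

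**State (c).** The condition for resuming has not been met, and 4.6 names an endpoint without resumption. As drafting, the specific rule answers the case; 4.1 merely fails to say so.

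**Scale per patient.** Inputs are 10 doses over 5 days (4.2), a tracing 24-48 h after the first dose (4.5) and a 24-hour hold (4.6). I assume 12-hour spacing, so dose k falls at 12 × (k − 1) h and the tenth at 12 × 9 = 108 h after the first.

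- State (a), tracing at 24 h: earliest resumption 24 + 24 = 48 h. Slots left: (108 − 48)/12 + 1 = 6.
- State (a), tracing at 48 h: earliest resumption 48 + 24 = 72 h. Slots left: (108 − 72)/12 + 1 = 4.
- State (b), stop at 48 h: 4 or 5 doses taken, depending on whether the 48 h dose was given, so 10 − 5 = 5 or 10 − 4 = 6 remain unused.

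The state (a) counts are upper limits for tracings in the routine window. A later qualifying repeat, or doses taken in hospital after resumption, lowers them. A clinical tracing before 24 h could raise them.

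**Number of patients.** The documents give neither the rate of discharge before completing drug, nor the rate of QTc above 500 ms, nor how often the 24-48 h tracing is missed. No count follows from them.

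**The case against.** The strongest reply is that 4.1 is dispensing logistics, while 4.6 is the dedicated and mandatory section on stopping drug. A reader might infer that 4.1 overrides the QTc stop. The documents do not support that: nothing gives 4.1 precedence, and the same logic would have it restart drug stopped for an adverse event. This disposes of state (c) apart from the missing exception. It does not settle state (a), where 4.6 itself directs dosing but attaches checks that are not provided for after discharge.

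On state (b), 4.5 is a deliberate allowance for early leavers, and the limit to hospitalized patients in 4.6 looks drafted to match it. That is fair for a patient who leaves before the window closes. Nothing shows that the allowance was meant to undo a stop already imposed under 4.6.

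Appendix A also omits the conditional inpatient repeat EKGs, so its silence does not exclude a tracing after discharge. That stands, and it is why the claim is that no such check is provided for, not that none could be done.

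A reader might also infer that the safety comparison between arms becomes unreliable. Treatment is blinded, randomization is stratified by site and analysis is by intention to treat. Different site readings could alter exposure in a few patients, but they are not a source of imbalance between arms. Nor is 9.2 shown to be wrong: it is a summary, does not promise a QTc for every patient, and the early-discharge allowance is stated openly in 4.5.

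**Conclusion.** The point holds for two discharge states. In (a), mandatory instructions in 4.1 and 4.6 cannot both be followed under the scheduled procedures. In (b), 4.1 and 4.5 can be read to permit dosing that 4.6 had stopped. State (c) is a missing exception, since 4.6 is best read as controlling. Unmonitored dosing is a possible result of the text, not something it instructs. None of this says which rule is clinically right.

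Per patient, a handful of doses is involved: up to 4 to 6 slots after resumption, or 5 to 6 unused doses after a stop for a missing tracing, assuming 12-hour spacing and a tracing or stop tied to the routine window.

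The number of patients is unknown and probably small. A reader might be tempted to multiply an assumed early-discharge rate by an assumed QTc rate over 510 patients. That would count people who leave before any tracing, whom 4.5 covers, and would treat discharge and a QTc hold as independent, which is doubtful. Nor can an even split between arms be assumed, because 9.1.1 says that hydroxychloroquine can prolong the QT interval. The case for change rests on conflicting text around a patient-safety stop, not on a count.

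**What to change.** Reconcile 4.1, 4.5 and 4.6 so that one stated rule covers a patient discharged (i) during a hold for QTc above 500 ms, (ii) after resumption while daily QTc assessments are still due, and (iii) after a stop because the 24-48 h QTc could not be assessed. Make the packet sentence in 4.1 subject to that rule. The clinical content is for the sponsor and DSMB.

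The sponsor can count affected patients from data already planned: QTc values and decisions to continue or stop drug (4.6), discharge times (6.2), and missed doses reported by telephone (6.3.1).

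The cost is a protocol wording change and one line on a discharge checklist, plus whatever follows from the rule the sponsor chooses.
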